3.5.2. Adverse Events (AEs)

AE information will be collected from treatment initiation and continues throughout the study until end of participation (refer to Section 7.1.1 of the protocol).

[figure not shown]
The reported AE term will be coded using the current version of the MedDRA. The severity of AE will be presented as reported by the investigator based on National Cancer Institute Common Terminology Criteria for Adverse Events (NCI CTCAE) grades version 4.03.

Incidence of AEs will be tabulated by SOC and PT for:

- All AEs
- AEs by relationship to study treatment and maximum severity grade
- AEs with action taken drug interrupted
- AEs with action taken dose reduced
- AEs with action taken drug withdrawn
- Serious Adverse Events (SAE)
- AEs leading to deaths – An AE is considered as leading to death if CTCAE Grade 5 is reported.

In the event a patient experiences repeated episodes of the same AE according to PT, the event with the highest severity grade to study treatment will be used for purposes of incidence tabulations.

Detailed listings for all AEs will be provided.

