Subjects will be treated in the assigned cohort until progressive disease based on irRECIST, unacceptable toxicity, consent withdrawal or the Investigator concludes that it is in the subject's best interest to discontinue (or any other withdrawal criteria is met according to section 5.5). Subjects who discontinue treatment for reasons different than irPD will enter the follow-up phase and will continue to be followed with tumor assessment every 12 weeks until irPD. After irPD, and provided that subject has undergone the End of Treatment visit, all subjects will be taken off the study unless presence of serious adverse events (SAEs) or study treatment-related adverse events. In such case these events will be monitored as clinically indicated until the events have resolved (or return to baseline) or in the Investigator's opinion, are unlikely to resolve due to the nature of the condition and/or the subject's underlying disease.

Once 5 subjects in each cohort are considered evaluable, enrollment will be stopped and data from each cohort will be analyzed and the optimal schedule to be taken forward into Part B will be selected according to section 3.3.

Part A includes mandatory tumor core biopsies for biomarkers research and mandatory whole blood sampling for DNA methylation analyses (see section 6.4.7).

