5: There is no window to obtain the signed and dated PICF. Study specific screening assessments not considered standard practice by the institution must start only once the PICF has been signed. Registration takes place as soon as the subject signs the PICF. After screening procedures and if subject meets all eligibility criteria, enrollment will be done according to the process described in section 6.1.2.1.

6: Only in women of childbearing potential. Refer to section 4.1 for definition of women of childbearing potential.

7: Hematology: Hemoglobin, Absolute Neutrophils Count (ANC), Platelets. Blood chemistry: creatinine, AST, ALT, alkaline phosphatase, total bilirubin, glucose, TSH. There is no need to repeat hematology and blood chemistry prior to first dose of study treatment provided that they were done at screening within 7 days of enrollment, unless deemed clinically required by the Investigator. During treatment period hematology will be done within 3 days of every visit prior to each CC-486 cycle and on Days 8, 15 and 22 (\pm 1 day). Blood chemistry will be done within 3 days of every visit prior to each CC-486 cycle. There is no need to repeat them prior to pembrolizumab administration unless clinically indicated and/or required according to the standard of care at the

institution.

8: There is no need to repeat CA-125 prior to first dose of study treatment provided that it was done at screening within 7 days of enrollment. Whenever possible, CA-125 should be tested at the same laboratory and with the same technique throughout the study. At the End of Treatment visit and during the follow-up, CA-125 will only be tested in subjects without irPD at time of study treatment discontinuation.

9: During the follow-up phase, only SAEs (regardless of the relationship to study drugs) and non-serious AEs related to study treatments are to be reported and/or followed up (refer to section 6.3.4).

10: Concomitant treatments to be collected from date the PICF is signed

11: Only concomitant treatments to treat AEs related to study treatment and SAEs (regardless of their relationship) will be recorded after the End of Treatment visit

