7. SAFETY MONITORING

7.1 Definitions

7.1.1 Period of Observation

At each visit and any contact during the study and follow-up period, the Investigator or designee will inquire about the occurrence of AEs and will document them in the subject file.

The Investigator or designee will report the AEs in the eCRF and to TRIO Drug Safety and Pharmacovigilance Department when required as per the table below:

Table 8: Reporting period of AEs/SAEs

Study period	AEs (non-serious)		Serious Adverse Events/Pembrolizumab Events of Clinical Interest (ECI)	
	Part A	Part B	Part A	Part B
From PICF to first dose	Not required to report	Only if related to study participation	Only if related to study participation	Only if related to study participation
Study treatment period until End of Treatment visit	All (regardless of relationship)	All (regardless of relationship)	All (regardless of relationship)	All (regardless of relationship)
From End of Treatment visit until End of subject participation ¹	Only if related to study treatment	Only if related to study treatment)	All (regardless of relationship)	Only if related to study treatment

¹ The applicable events as per the table that are ongoing at time of the End of Treatment visit should be followed up to resolution or until the event becomes stable (or returns to baseline) or is unlikely to resolve further in the opinion of the Investigator. Regarding SAEs, in Part A all should be reported/ followed after the End of Treatment visit, regardless of the relationship with the study drugs. In Part B, only study-drug related SAEs should be followed/ reported.

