3.1.2. Safety Population

The **Safety Population** consists of all patients who receive any study treatment, and will be used for the analysis of safety data of the study. This population will assign patients to the cohort based on the treatment schedule observed in Cycle 1. If this differs from that to which the patient was enrolled, the actual observed treatment schedule will be used for the analysis of safety data.

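### The Part A AE tables pool events up to the End of Treatment visit with later events that are collected selectively, so crude All-AE, SAE and grade 5 incidence by cohort depends partly on why subjects stopped.

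*SAP*

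**What the plan says.** **SAP.** Section 3.5.2 describes the span as "AE information will be collected from treatment initiation and continues throughout the study until end of participation" and refers to protocol 7.1.1. It continues with "Incidence of AEs will be tabulated by SOC and PT for" all AEs, related AEs, SAEs, AEs leading to death and other subsets. The denominator is the Safety Population, which "consists of all patients who receive any study treatment, and will be used for the analysis of safety data of the study". Neither 3.5.2 nor the planned outputs in section 5 define a treatment-emergent period, an End of Treatment cut or a post-treatment table.

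**Protocol, what is collected.** Table 8 in section 7.1.1 has one row for "Study treatment period until End of Treatment visit", in which all AEs and SAEs are reported whatever the cause. A second row, "From End of Treatment visit until End of subject participation", is narrower. Footnote 9 to Table 6 gives the Part A rule: "During the follow-up phase, only SAEs (regardless of the relationship to study drugs) and non-serious AEs related to study treatments are to be reported".

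**Protocol, who is followed.** In Part A (sections 6.3.3 and 6.3.4.1), the End of Treatment visit is the last visit, with two exceptions: subjects who stopped for a reason other than irPD, and subjects with an ongoing SAE or related AE at that visit. Section 3.1 says "After irPD, and provided that subject has undergone the End of Treatment visit, all subjects will be taken off the study", with an exception for SAEs or related AEs. Footnote 12 to Table 6 continues tumor assessment to irPD even after subsequent anticancer therapy has started.

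**The concern.** One crude percentage is formed from two kinds of observation. Before the End of Treatment visit, ascertainment is complete for all treated subjects. After it, ascertainment is partial by event type and by subject, yet the denominator still counts everyone treated.

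Entry to the later period is not random. One group is defined by the reason for stopping and the other by toxicity already present. Both can differ between schedules for reasons written into the protocol. Table 3 allows no CC-486 dose reduction in Schedule 1, one in Schedule 2 and two in Schedules 3 and 4. Under Table 5 the same grade 3 or 4 non-hematologic event can therefore end CC-486 in one schedule and lead to a reduction in another. Section 5.5 ends both drugs when either is permanently stopped.

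Choosing the schedule is the primary objective of Part A. Step 2 of protocol 3.3 rests on the toxicity profile together with irORR. A difference in SAE or grade 5 incidence between cohorts could partly reflect who was still being watched, or events under a later therapy.

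**Working it through.** The documents give no AE rate or expected share of subjects followed, so there is no plan figure to reproduce. The check is a comparison of the sections, followed by an illustration on assumed values.

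**Step 1: collection on each side of the End of Treatment visit, Part A**

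| Event type | First dose to End of Treatment visit | After End of Treatment visit |
|---|---|---|
| Non-serious, unrelated | All treated subjects | Not collected |
| Non-serious, related | All treated subjects | Only subjects still followed |
| SAE, any cause | All treated subjects | Only subjects still followed |

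Sources: protocol Table 8; Table 6 footnotes 3, 4 and 9; sections 6.3.3 and 6.3.4.1.

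**Step 2: which tables are touched.** The All-AE table is affected both by event type and by who is followed. The SAE, related and grade 5 tables are affected only by who is followed.

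**Step 3: weight of one event.** SAP 2.3 sets a minimum of five patients per cohort. One subject with an event is then at most 1/5 = 20 percentage points. In a larger cohort it is less.

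**Step 4: illustration (assumed values, not trial figures).** Let p0 be the incidence up to the End of Treatment visit, q the chance that a subject without an event by then has a first one later if watched, and f the share of subjects watched. Assume q is the same whether or not a subject is followed. Then

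incidence as planned = p0 + (1 − p0) × q × f.

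With p0 = 20% and q = 30%:
- f = 0.2: 0.20 + 0.80 × 0.30 × 0.2 = 24.8%
- f = 0.5: 0.20 + 0.80 × 0.30 × 0.5 = 32.0%
- f = 0.8: 0.20 + 0.80 × 0.30 × 0.8 = 39.2%
- everyone followed: 0.20 + 0.80 × 0.30 = 44.0%
- cut at End of Treatment: 20.0% whatever f is

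With q = 10% the planned figure runs from 21.6% (f = 0.2) to 26.4% (f = 0.8), against 28.0% with everyone followed. With p0 = 40% it runs from 41.2% to 44.8% for q = 10%, and from 43.6% to 54.4% for q = 30%.

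Two cohorts with identical risk can therefore show different incidence because f differs. The gap ranges from a few points to about 14 over these assumptions.

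**The case against.** The strongest reply is that this is a matter of presentation and not an error. The sentence in SAP 3.5.2 is about collection, and the protocol openly sets out the periods. A figure follows that sentence in the SAP and is not shown; it may repeat them. The AE listings carry onset date, seriousness, grade and relationship. The death listing gives days from last dose, and on-study anticancer therapy is listed with dates. With about five subjects per cohort and purely descriptive tables, the Steering Committee could pick out each late event by hand. The full selection criteria sit in its Charter, which is not among the documents.

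Much of this stands. The documents do not contradict each other, and that the tables cover the whole span is an inference. It is a fair one, because the SAP states no other AE window. The listings make a split possible, but the plan does not call for one.

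Several stronger readings are tempting, and the documents do not support them:
- **That later SAEs come only from subjects who stopped without irPD.** Subjects who stop for irPD are also followed if an SAE or related AE is ongoing.
- **That unrelated SAEs under later therapy could reject a cohort.** Step 1 of protocol 3.3 counts only AEs related to study drugs. Disease progression and death from it are generally not reported as SAEs (7.1.3.1).
- **That the related share of AEs is inflated.** No table of that share is planned.
- **That the excess follow-up can be sized from the irPFS medians of 4 and 6.4 months in protocol 8.7.** These are Part B assumptions, and the lower one is for pembrolizumab alone, which no Part A cohort receives. The Part A analysis starts once five subjects per cohort are evaluable, which shortens follow-up for later entrants.
- **That Part B has the same fault.** There all subjects are followed (6.3.4.2), only related events are reported after End of Treatment, and the analysis has its own plan.

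**Conclusion.** The point holds for Part A. As written, the between-cohort All-AE, SAE and grade 5 figures combine complete ascertainment up to the End of Treatment visit with selective ascertainment after it. They therefore depend partly on why subjects stopped. The conclusion rests on two readings: that the SAP tables cover the only AE span the SAP states, and that reasons for stopping can differ by schedule under the protocol's own dose rules. The documents fix neither the direction nor the size of any distortion. What they do fix is the scale: up to 20 percentage points per event in a cohort of five. The consequence is for the toxicity comparison in Step 2, not for rejection in Step 1 through unrelated events. It is worth correcting because the split is cheap and the affected comparison serves the primary objective of Part A.

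**What to change.** In SAP 3.5.2 and the planned outputs:

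1. Make onset from first dose through the End of Treatment visit the main window for the between-cohort AE tables.
2. Tabulate later-onset events separately by cohort (related AEs, and all SAEs). Show the number of subjects followed after End of Treatment, and flag whether subsequent anticancer therapy had started before onset.
3. State which window feeds the toxicity criteria in protocol 3.3, so that late related events are not lost from them. Those criteria currently give no time window.
4. Add a rule for partial onset dates that could fall on either side of the visit. The present imputation rules are anchored on first dose only.

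The cost is SAP wording and one additional table; no new data are collected and no event is discarded. The downside is that the protocol itself expects some immune-related events several months after the last dose (5.7.2.2). These move to the second table and must be read from there.

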3.5.3. Laboratory Values

Lab values will be converted to standard units and categorized according to NCI CTCAE version 4.03. Laboratory results not corresponding to NCI CTCAE terms will not be graded.

Hematology and serum blood chemistry will be summarized in descriptive statistics by calculating the mean, standard deviation, median, and range for the following:

- Baseline value
- Minimum post baseline value
- Maximum post baseline value

Shift tables in laboratory toxicity grades (comparing baseline grade with worst post-baseline grade) will be analyzed using standard shift tables, presenting number and proportion of patients and their maximum grade shift.

For laboratory tests without a toxicity grading scale, the shift table will present directional shifts from baseline to above or below the laboratory standard normal range using the maximum increase and/or decrease observed throughout the course of treatment/observation.

3.5.4. ECOG Performance Status

Descriptive statistics of ECOG Performance Status results will be done for the following:

- Baseline value
- Minimum post baseline value
- Maximum post baseline value

A shift table will be provided as well from baseline status to the worst status of post-baseline time points.

3.5.5. Concomitant Medications

CM and on study systemic anti-cancer therapies are coded to the current version of World Health Organization Drug Dictionary (WHODD). The preferred name will be tabulated and listed by patient.

3.5.6. Death

All deaths will be reported in a patient listing, which will include date of death, date of last dose, the primary cause of death, and the number of days between the date of last dose to study drug and death.

4. Study Steering Committee (SSC)

The result of statistical analysis will be reviewed by SSC who is responsible for the scientific conduct and integrity of the trial. SSC will review the results and act in correspondence to the SSC Charter.

5. List of Planned Statistical Outputs

5.1. Planned Tables

Title	Population	Description
Patient Disposition	ITT	Tabulates the disposition of all patients by cohort, including the number of patients in each population set, discontinued from study treatment, and discontinued from study. The reason for drug discontinuation and study discontinuation will also be summarized.
Protocol Deviations	ITT	Tabulate the number of patients who reported protocol deviations by deviation category for each cohort.
Eligibility Deviations	ITT	Tabulates the number of patients who violates inclusion/exclusion criteria by criterion for each cohort
Patient Demographics	ITT Safety	Tabulates summary statistics of patient demographics (age, race, ethnicity, weight and ECOG status at baseline) for each cohort.
Disease Characteristics	ITT	Tabulates summary statistics for time from initial diagnosis to enrollment, primary tumor location, staging at initial diagnosis, histopathological type at initial diagnosis, histopathological grade at initial diagnosis, disease status at enrollment, time from first progression/relapse to enrollment for each cohort.
Prior Surgery for Ovarian Cancer	ITT	Tabulates the number of patients with type of procedures for each cohort.
Prior Systemic Anti-Cancer Therapy	ITT	Tabulates the number of regimens received by patient according to type and indication of the systemic cancer therapy for each cohort.
Medical History	ITT	Summarizes medical history by SOC and PT for each cohort.
Study Drug Exposure	Safety	Summarizes the number of cycles, the duration of treatment, cumulative dose, and RDI by cohort. The number of dose modification will also be summarized by study drug.

Title	Population	Description
Compliance	Safety	CC-486 Compliance assessment will be summarized by each cycle.
Best Overall Response/irORR and irDCR	ITT	Summary of Best Overall Response as per irRECIST will be tabulated by cohort irORR and irDCR will also be reported
CA-125	ITT	Summary of CA-125 Response Rate will be tabulated by cohort.
AEs Overview	Safety	Tabulates the number of patients with AEs, Related AEs, Grade 3 / 4 AEs, AEs with action taken dose reduced, AEs with action taken drug interrupted, AEs leading to drug withdrawn, SAEs, Fatal AEs.
AEs	Safety	Summary by SOC and PT of number of patients and events for each cohort.
Related AEs – CC-486	Safety	Summary by SOC and PT of number of patients and events for each cohort.
Related AEs – Pembrolizumab	Safety	Summary by SOC and PT of number of patients and events for each cohort.
SAE	Safety	Summary by SOC and PT of number of patients and events for each cohort.
Grade 3 / 4 AEs	Safety	Summary by SOC and PT of number of patients and events for each cohort.
Grade 5 AE	Safety	Summary by SOC and PT of number of patients and events for each cohort.
AEs with Action Taken as Dose Reduced – CC-486	Safety	Summary by SOC and PT of number of patients and events for each cohort.
AEs with Action Taken as Drug interrupted – CC-486	Safety	Summary by SOC and PT of number of patients and events for each cohort.
AEs with Action Taken as Drug interrupted – Pembrolizumab	Safety	Summary by SOC and PT of number of patients and events for each cohort.
AEs Leading to Drug Withdrawn – CC-486	Safety	Summary by SOC and PT of number of patients and events for each cohort.

Title: [Redacted] TRIO026 (Part A) – Statistical Analysis Plan

Title	Population	Description
AEs Leading to Drug Withdrawn – Pembrolizumab	Safety	Summary by SOC and PT of number of patients and events for each cohort.
Laboratory Values	Safety	Summary of each laboratory parameter at baseline, minimum post baseline value, and maximum post baseline value for each cohort. In addition, shift tables will be presented.
ECOG Performance Status	Safety	Summary of ECOG performance status at baseline, minimum post baseline value, and maximum post baseline value for each cohort. In addition, a shift table will be presented.
Concomitant Medications	Safety	Tabulate the frequency and percentage of patients according to preferred name. Summary will be presented separately for concomitant medications and on study systemic anti-cancer therapies.

5.2. Planned Listings

Title	Population	Description
Patient Accountability	ITT	Listing of all patients and with population indicators. For patients who discontinued from treatment and/or study, include the reason of respective discontinuations.
Deaths	ITT	Listing of patients who died, including primary cause of death, date of death, date of last dose, and the number of days from date of last dose to death.
Patient Demographics	ITT	Listing of patient demographics.
Disease Characteristics	ITT	Listing of disease characteristics.
Prior Surgery for Ovarian Cancer	ITT	Listing of prior surgery for ovarian cancer.
Prior Systemic Anti-Cancer Therapy	ITT	Listing of prior systemic anti-cancer therapy.
Study Drug Exposure	Safety	Listing of patients for extent of exposure by cycle.

Title	Population	Description
Study Drug Exposure Summary	Safety	Listing of patients for summary of exposure (e.g. number of cycles, duration of treatment, cumulative dose, dose intensity, RDI).
Efficacy Parameters	ITT	Listing of best overall response for each patient
Tumor Assessment	ITT	Listing of tumor assessment including lesion number, date of assessment, lesion measurement/response, and time-point overall response.
CA-125	ITT	Listing of CA-125 reported for each patient.
AEs	Safety	Listing of all AEs for each patient; the listing includes the verbatim term, PT, SOC, seriousness, worst grade, start date, outcome, stop date, relationship to study drug, and action taken for study drug.
Related AE – CC-486	Safety	Listing of AEs in this category using the same structure as the AEs listing.
Related AE – Pembrolizumab	Safety	Listing of AEs in this category using the same structure as the AEs listing.
SAEs	Safety	Listing of AEs in this category using the same structure as the AEs listing.
Grade 3 / 4 AE	Safety	Listing of AEs in this category using the same structure as the AEs listing.
AEs Leading to Death	Safety	Listing of AEs in this category using the same structure as the AEs listing.
AEs with Action Taken for Dose Reduced – CC-486	Safety	Listing of AEs in this category using the same structure as the AEs listing.
AEs with Action Taken for Drug Interrupted – CC-486	Safety	Listing of AEs in this category using the same structure as the AEs listing.
AEs with Action Taken for Drug Interrupted – Pembrolizumab	Safety	Listing of AEs in this category using the same structure as the AEs listing.
AEs Leading to Drug Withdrwan – CC-486	Safety	Listing of AEs in this category using the same structure as the AEs listing

Redacted line of text containing several black rectangular boxes.

Title: TRIO026 (Part A) – Statistical Analysis Plan

Title	Population	Description
AEs Leading to Drug Withdrawal – Pembrolizumab	Safety	Listing of AEs in this category using the same structure as the AEs listing
Laboratory Values	Safety	Listing of all laboratory values and their assigned toxicity grade (where applicable).
ECOG Performance Status	Safety	Listing of ECOG at each assessment.
Concomitant Medications	Safety	Listing of verbatim product name, preferred name, start date, end date (or ongoing) and indication.
On Study Systemic Anti-Cancer Therapies	Safety	Listing of regimen number, verbatim product name, preferred name, type of therapy, start date, end date (or ongoing)

